7.6 Analysis of Efficacy

7.6.1 *Analyses Supporting the Primary Efficacy Endpoint*

7.6.1.1 *Treatment Success*

A hierarchical, closed-testing procedure will be utilized for the primary endpoint and secondary endpoints. Analyses of the single primary endpoint, recurrence of CDI within 8 weeks of blinded treatment, will be analyzed as the proportion of treatment success of Group A Placebo (P_{PLA}) and Group B RBX2660 (P_{RBX}). This analysis will be performed on the ITT, mITT and PP populations, with the mITT being the analysis of import for reporting purposes.

The primary efficacy analysis will be a Bayesian hierarchical model which formally incorporates data from the previous Phase 2B study (Protocol 2014-01) of RBX2660. Study success will be declared if the posterior probability of superiority exceeds 0.99943 at the first two interim analysis. If the trial continues to the maximum enrollment, the success criteria will be chosen so that the overall alpha is a nominal 0.00125. Success at this level is considered appropriate for approval based on results from a single study. If success at this level is not met at the final analysis, success may also be declared if the posterior probability exceeds 0.97706. Success at this secondary threshold still constitutes a successful study, although it may not be sufficiently strong evidence to request regulatory approval based on a single study without further FDA discussion. Details regarding the analysis can be found in Section 10 (Bayesian Analysis Plan).

The secondary endpoints will be analyzed using a hierarchical testing approach if sufficient evidence is found to claim study success.

The primary efficacy analysis will be conducted when all subjects in each group reach their 8-week assessment following blinded treatment or early termed from the study. Full study results in the form of a final analysis and report will be completed once the last subject has completed the 6-month telephone assessment, at which time the study will be considered complete. This includes subjects receiving unblinded RBX2660 due to a documented treatment failure.

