The primary goal of the trial is to demonstrate the efficacy of RBX2660 by testing the hypothesis:

$$H_0: TE \leq 0 \quad \text{vs.} \quad H_A: TE > 0$$

We test this hypothesis by calculating the posterior probability of superiority, $\Pr(TE > 0 | \text{Data})$, which is equivalent to $\Pr(\theta_1 > 0 | \text{Data})$. The thresholds for defining success at each analysis are summarized in Table 2.

Table 2: Success criteria at each analysis. The * indicates that the success criteria may be updated at the final analysis to ensure the correct amount of α –spend.

Analysis	Criteria	Subjects complete
Interim 1	$\Pr(TE > 0 \text{Data}) > 0.99943$	Minimum 160
Interim 2	$\Pr(TE > 0 \text{Data}) > 0.99943$	220
Final	$\Pr(TE > 0 \text{Data}) > 0.99943^*$	Maximum 270
Final	$\Pr(TE > 0 \text{Data}) > 0.97706$	Maximum 270

The success criteria of 0.99943 was chosen using a Pocock spending function for analysis performed at 160, 220, and 270 patients complete with a cumulative α spend of 0.00125. Success at this level is considered appropriate for approval based on results from a single trial.

Uncertainty from several factors make assessing the exact α –spend at each analysis difficult to quantify. First, the definition of the mITT population allows for the final analysis to be performed with fewer than 270 complete subjects. In addition, the first interim analysis may be performed when more than 160 subjects are enrolled and treated. Finally, the second interim analysis may be omitted if the first interim analysis occurs sufficiently close to 220 subjects enrolled. Therefore, to account for this uncertainty, the success criteria at the final analysis will be updated to reflect the information spend at each interim analysis and ensure a cumulative α spend of 0.00125. This change will be made based on the fraction of information at each interim analysis and does not depend on the outcome data for the trial.

The lower, secondary, threshold of 0.97706 at the final analysis allows for success at the less demanding $\alpha = 0.025$ level. The second threshold at the final analysis controls the overall Type I error rate for the trial at 2.5% (without borrowing), accounting for the α spend at the interims and higher look at the final analysis.

Futility Stopping

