In this example, the first interim analysis occurs when 180 subjects have been enrolled. The observed control rate is 0.5, somewhat higher than seen in the Phase 2b trial. Example 3.1 shows the status of the trial at the first interim

[figure not shown]
Example 3.1: Status of the trial at the 1st interim

The posterior estimate of the control response rate (0.473) is somewhat lower than

[figure not shown]
observed due to the borrowing and the posterior probability of a treatment effect is insufficiently high to declare success at the first interim.

Example 3.2: Status of the trial at the 2nd interim

At the second interim (N=220, shown in Example 3.2), the observed response rates in both arms have been reduced. The trial has not shown sufficient evidence to declare success or futility and continues enrollment, though the predictive probability of success at the final analysis remains optimistic (0.797).

Example 3.3: Status of the trial at the final analysis

The final analysis is conducted when 270 patients have completed follow-up and 260 subjects qualify for the mITT population (Example 3.3). The single trial success criteria is updated to 0.99931, using the information fraction and 0.99943 criteria at the first two interims (0.692 and 0.846) to ensure an overall α –spend of 0.00125. The trial is declared a success at the 0.025 level, though it does not meet the single trial success criteria.

Performance Characteristics

The performance characteristics of the design were determined through trial simulation. We assume several scenarios for the underlying response probability for the control and treatment arms, considering control probabilities in $\{0.2, 0.3, 0.4, 0.45, 0.5, 0.6, 0.7\}$ and additive treatment effects of $\{0.0, 0.05, 0.1, 0.15, 0.2, 0.25, 0.3\}$. The scenario with a control probability of 0.45 and a treatment effect of 0.15 corresponds most closely to what was observed during the Phase 2b trial. The scenarios with treatment effects of 0 correspond to null scenarios. For the purposes of simulation, we assume that patients are randomized in 3 patient blocks, that interim analysis were performed with exactly 160 and 220 subjects completed, and that the 270 mITT subjects have complete data at the final analysis.

Operating Characteristics

We simulated 1,000,000 virtual trials for each scenario. The results of the simulations are summarized using the following operating characteristics.

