- **Pr(Success):** the cumulative probability of declaring success at the analysis. For example, Pr(Success) under the section Interim 2 includes the probability of declaring success at either Interim 1 or Interim 2. For the final analysis, Pr(Success) (0.99943) and Pr(Success) (0.97706) include the cumulative probability of declaring success at the single trial and lower success levels respectively.
- **Pr(Futility):** the cumulative probability of declaring futility at the analysis
- **# Subjects:** the average number of subjects enrolled in the trial
- **Bias:** the average error in estimating the true (simulated) treatment effect.

Table 4 shows an example set of operating characteristics when the simulated control response probability is 0.45.

Table 4: Operating characteristics of the design when the underlying control response probability is 0.45.

Effect	Interim 1		Interim 2		Final analysis	
	Pr(Success)	Pr(Futility)	Pr(Success)	Pr(Futility)	Pr(Success) (0.99943)	Pr(Success) (0.97706)
0	0.001	0.445	0.001	0.732	0.002	0.042
0.05	0.006	0.204	0.012	0.424	0.018	0.204
0.1	0.037	0.065	0.072	0.158	0.106	0.528
0.15	0.141	0.014	0.257	0.036	0.354	0.833
0.2	0.363	0.002	0.564	0.005	0.695	0.969
0.25	0.651	0.000	0.838	0.000	0.919	0.997
0.3	0.868	0.000	0.965	0.000	0.989	1.000

Under the null scenario where both the control and treatment arms have a 45% true response rate, 45% of trials stop for futility at the first interim analysis ($N = 160$) and 0.1% of trials meet the success criterion. By the second interim, 73% of trials have stopped for futility. Assuming a final threshold of 0.97706, the probability of trial success at or before the final analysis is 0.042. The type I error of this trial is inflated beyond the nominal 2.5% level because of the borrowing from the positive phase 2 data.

In the scenario with a treatment effect of 0.15 (which most closely reflects the observed data from Phase 2), the trial has 83% power. Broken down by analysis, 14% of trials declare success at the first interim, another 12% of trials declare success at the second interim, 9% of trials reach the higher success threshold of 0.99875 at the final analysis and 48% of trials declare success at the lower hurdle at the final analysis. When the true

[figure not shown]
effect is 0.10, the overall power drops to 52% with 77% of trials progressing to the final analysis.

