Operating characteristics for simulations with control response probabilities in $\{0.2, 0.3, 0.4, 0.5, 0.6, 0.7\}$ are included at the end of this section.

Decision Rules

The decision rules of the trial at each analysis can be characterized in terms of the observed effect sizes (# responders / # subjects enrolled) in each arm. The effects leading to either futility or success, colored by result, are shown in Figure 2.

Figure 2: Scatterplots of the observed response rates for both arms, colored by result.

The design has a clear decision boundary at the first interim, declaring futility or success when the observed treatment effect is sufficiently large or small. The gap between success and futility narrows at the 2nd interim, as more information about the arms informs decision making. The effect size required to win is smallest at the final interim.

Operating Characteristics with No Borrowing

For comparison we include the operating characteristics of an alternate design without borrowing. This design uses the same interim schedule as the borrowing design but does not include stopping for futility. Table 6 compares the cumulative probability of declaring success for at each interim for both designs when the simulated control response rate is 0.45.

Table 6: Operating characteristics for the borrowing design (borrow) and alternate design (none) at each interim analysis when the simulated response rate is 0.45.

Effect	Interim 1		Interim 2		Final (0.99943)		Final (0.97706)	
	Borrow	None	Borrow	None	Borrow	None	Borrow	None
0	0.001	0.000	0.001	0.001	0.002	0.001	0.042	0.022
0.05	0.006	0.004	0.012	0.007	0.018	0.010	0.204	0.106
0.1	0.037	0.019	0.072	0.038	0.106	0.059	0.528	0.320
0.15	0.141	0.072	0.257	0.141	0.354	0.212	0.833	0.629
0.2	0.363	0.202	0.564	0.362	0.695	0.496	0.969	0.877
0.25	0.651	0.429	0.838	0.655	0.919	0.794	0.997	0.977
0.3	0.868	0.693	0.965	0.883	0.989	0.955	1.000	0.998

For a simulated treatment effect of 0.15, the borrowing design has 20% more power than the alternate design. Broken down by interim, the borrowing design is 7% more likely to declare success at the first interim, 12% more likely to declare success by the second interim, and 14% more likely to reach the higher threshold by the final analysis. The borrowing design is more likely to declare success when the simulated treatment effect is 0, with a 4.2% chance of declaring success compared to 2.2% for the alternate design.

Operating Characteristics Under Drop Out

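### The 0.00125 alpha that the SAP attaches to the single-trial success criterion is calculated without borrowing and is not the type I error of the borrowing rule that decides success

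*SAP*

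**What the plan says.** SAP Section 7.6.1.1 applies a posterior-probability threshold of 0.99943 at both interims to a hierarchical model that borrows from Protocol 2014-01. For the final analysis it says "the success criteria will be chosen so that the overall alpha is a nominal 0.00125", and it regards success at this level as suitable for approval on one study. A lower threshold of 0.97706 also counts as success at the final analysis.

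The appendix, under Success Criteria, derives 0.99943 from a Pocock function with looks at 160, 220 and 270. It says the final criterion will be updated to "ensure a cumulative α spend of 0.00125". On the method it says: "This change will be made based on the fraction of information at each interim analysis". Example 3.3 carries this out for a borrowing analysis and arrives at 0.99931.

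For the lower tier the appendix is explicit about the basis: "The second threshold at the final analysis controls the overall Type I error rate for the trial at 2.5% (without borrowing"). Under Operating Characteristics it adds: "The type I error of this trial is inflated beyond the nominal 2.5% level because of the borrowing from the positive phase 2 data". The comparison with a no-borrowing design reports the lower tier at a control rate of 0.45 "with a 4.2% chance of declaring success compared to 2.2% for the alternate design". No sentence of this kind accompanies the 0.00125 tier.

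**The concern.** A reader of Section 7.6.1.1, or of the word *ensure* in the appendix, will take 0.00125 as the false-positive rate of the rule that decides success. That rule uses 19/44 placebo and 25/42 single-dose responders from Phase 2b, which favour the product. Its error rate therefore depends on where the Phase 3 placebo rate falls relative to the Phase 2b rate of 0.432. An update based only on information fractions cannot account for that. The figure matters because it supports the claim that one study is enough. Labelling one tier as calculated without borrowing, and leaving the other unlabelled, also invites the inference that 0.00125 is the attained rate.

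**Working it through.** **1. Reproduce 0.99943 with no Phase 2b data.** Take a one-sided group-sequential normal test with information 160/270 = 0.593, 220/270 = 0.815 and 1, and a constant boundary z = Φ⁻¹(0.99943), about 3.25. The cumulative null crossing probabilities are 0.00057, 0.00096 and 0.00126. Solving for exactly 0.00125 gives 0.999434, which rounds to the SAP's 0.99943.

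**2. Reproduce Example 3.3 the same way.** The fractions are 180/260 = 0.692 and 220/260 = 0.846. With 0.99943 at both interims, 0.00089 is spent by the second look. The final threshold that brings the total to 0.00125 is 0.99931, as printed. So 0.00125 is a no-borrowing calibration in both places.

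**3. Type I error of the borrowing rule.** Inputs from the appendix:
- Model: logit p(C,s) = α_s and logit p(T,s) = α_s + θ_s.
- Priors: N(0, 10²) on α and θ; inverse-gamma (location, weight) of (0.001, 0.1) and (0.01, 0.01) on the two variances.
- History: 19/44 and 25/42.
- Looks at 160, 220 and 270, randomized 2:1.

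Pr(θ₁ > 0 | data) was computed on a grid for every possible pair of responder counts. For p(C) = p(T) = p, exact binomial probabilities were then propagated through

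error(p) = P(cross at look 1) + P(first cross at look 2) + P(first cross at the final look).

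Check against the SAP: the lower-tier null values of 0.042 at 0.45 and 0.063 at 0.50 are recovered, and power at 0.45 versus 0.60 is 0.833 (SAP 0.833).

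Single-trial tier under the null:

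| Control rate | SAP table, with borrowing | Recomputed, with borrowing | Recomputed, without |
|---|---|---|---|
| 0.30 | 0.001 | 0.08% | – |
| 0.40 | 0.001 | 0.08–0.09% | – |
| 0.432 | not tabulated | 0.12% | 0.15% |
| 0.45 | 0.002 | 0.14–0.16% | 0.14% |
| 0.47 | not tabulated | 0.18–0.21% | 0.14% |
| 0.50 | 0.003 | 0.27–0.29% | 0.13–0.15% |
| 0.60 | 0.007 | 0.7% | 0.13% |
| 0.70 | 0.009 | 0.8% | – |

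The ranges reflect how the odd subject at 160 and 220 is allocated (106/54 or 107/53, and so on) and the grid step. The no-borrowing column is not exactly 0.125% because responder counts are discrete and the calibration uses normal theory. On the schedule of Example 3.3 (180/220/260, final threshold 0.99931), a rate of 0.47 gives 0.20% with borrowing and 0.14% without.

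**4. Can the final update secure 0.00125 for this rule?** At 0.47 the two interims alone give about 0.13% to 0.15% with borrowing, already above 0.125%. The SAP shows the same at 0.50: Table 9 prints a cumulative 0.002 by the second interim. The final threshold cannot recover error that has already been spent.

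**The case against.** Much of this is disclosed, and that part of the objection stands. The lower tier is labelled as calculated without borrowing, and its total includes the interim spend, so a careful reader can infer that the 0.00125 is on the same basis. Section 7.6.1.1 says *nominal* and refers to Section 10. The borrowing error of the single-trial tier is printed at seven control rates, with 0.002 against 0.001 at 0.45 in the no-borrowing comparison. The excess due to borrowing at 0.47 is small: 0.19% − 0.14% = 0.05 percentage points, about 5 extra false positives per 10,000 null trials. Comparing 0.19% with 0.125% gives a ratio of about 1.5, but that is not like for like; 0.19/0.14 is about 1.4.

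The objection does not rescue the statement itself. *Nominal* does not say that borrowing was left out, *ensure* suggests the opposite, and the tables contradict 0.00125 at control rates of 0.45 and above.

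Three stronger readings are tempting, and the documents do not support them:
- **The SAP conceals the inflation, or mislabels the 2.5% tier.** It states the basis, the cause and the size (4.2% against 2.2%). Example 3.3, where "The trial is declared a success at the 0.025 level, though it does not meet the single trial success criteria", reuses a level already defined as calculated without borrowing.
- **Borrowing always raises the error.** By the table above, it lowers this tier's error at 0.432 and is roughly neutral at 0.45.
- **The 2.5% in SAP 4.4 and Protocol 8.1 is wrong.** It belongs to the 240-subject sentence. A two-proportion test with 160/80, 69% versus 47% and one-sided 2.5% has 91.0% power, so the sentence is consistent as a trial-only calculation and needs no edit.

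**Conclusion.** The point holds, confined to the single-trial tier. The 0.00125 in Section 7.6.1.1, in Success Criteria and in Example 3.3 is a no-borrowing calibration, and the borrowing rule that decides success does not have that error rate in general. By the SAP's own tables the rate is 0.002 to 0.009 at control rates from 0.45 to 0.70. At the planning rate of 0.47 it is about 0.2%. Between about 0.30 and 0.43 it is below 0.125% (0.08% to 0.12%).

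The 0.47 figure assumes the stated priors, looks at exactly 160/220/270 and complete data. Futility stopping would lower the null results by at most 0.02 percentage points. Agreement with the SAP's third decimal is not perfect (0.8% against 0.009 at 0.70). With 10,000 iterations per simulated trial, the 0.99943 cut-off rests on about 10,000 × 0.00057 = 5.7 draws, so the sponsor's own run should supply the final number. This is a misstated error rate in the section that defines success; it is not a fault in the thresholds.

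**What to change.** 1. **SAP 7.6.1.1:** state that the overall alpha, *calculated without borrowing*, is a nominal 0.00125. Add that the type I error of the borrowing rule depends on the placebo rate and is given in Section 10.
2. **Appendix, text under Table 2 and Example 3.3:** in place of *ensure*, say that the final criterion is set so that the cumulative alpha spend calculated without borrowing is 0.00125.
3. **Beside that text:** give the attained single-trial-tier type I error with borrowing: 0.1% to 0.9% over control rates 0.2 to 0.7 (already tabulated), and about 0.2% at 0.47, to be confirmed by one added null scenario in the sponsor's simulations.

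SAP 4.4, Protocol 8.1 and the description of the 0.025 tier can stay as they are. The cost is a few clauses and one simulation scenario. Thresholds, futility rule, sample size and power do not change. The only downside is a slightly less favourable stated error rate.

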7.6.1.2 Sensitivity Analysis for the Primary Efficacy Endpoint

The primary efficacy analysis will be repeated using the ITT and PP population to assess the sensitivity of the primary endpoint regardless of the outcome of the mITT primary efficacy analysis. The ITT analysis will serve as the conservative analysis as it considers all subjects who exit prior to the 8-week efficacy assessment as treatment failures regardless of treatment failure documentation.

Three groups of sensitivity analyses will be performed to assess the sensitivity of the results to the borrowing of historical data from the previous Phase 2B study (Protocol 2014-01) of RBX2660.

- 1) A Pearson's chi-square test will be used to test the null hypothesis that the response rate in the treatment group is equal to that of the control group. In addition, two-sided 95% confidence intervals for the difference in response rate between arms will be calculated using a normal distribution approximation. This sensitivity analysis will be conducted using the mITT, ITT, and PP populations using data from the 2017-01 study only.
- 2) Sensitivity of the primary analysis (Bayesian analysis) to the analysis population (ITT, PP) using Bayesian analysis.
- 3) Sensitivity of the primary analysis (Bayesian analysis) to the following different sensitivity analysis populations from the 2014-01 study using Bayesian analysis. The **2014-01 Sensitivity Analysis Population #1** represents the ITT population from the 2014-01 study, and the **2014-01 Sensitivity Analysis Population #2** represents the

population used for the primary analysis inclusive of one subject in Group C who was exposed to product but did not receive the full enema.

2014-01 Sensitivity Analysis Population #1				2014-01 Sensitivity Analysis Population #2			
2014-01 Treatment Group	# Subjects	# Responders	Response Rate	2014-01 Treatment Group	# Subjects	# Responders	Response Rate
A	45	25	0.556	A	41	25	0.610
B	44	19	0.432	B	44	19	0.432
C	44	25	0.568	C	43	25	0.581

Efficacy analysis will be repeated without the borrowing of historical data from the Phase 2B study (Protocol 2014-01) using the mITT, ITT, and PP populations.

An analysis of time to CDI recurrence after completion of the assigned blinded treatment will be analyzed and presented by the Kaplan-Meier procedure and median duration presented by days (and weeks) using the ITT, mITT, and PP populations. The Kaplan-Meier estimate of the median time (days) and the associated 95% confidence interval will be presented for each treatment group. A graphic presentation of the Kaplan-Meier estimates will supplement the tabular presentation. Between group comparisons will be performed using the stratified log-rank test based on the stratification factor at randomization. The corresponding hazard ratio of the treatment effect along with the 95% confidence interval will be calculated using a Cox proportional hazard model with treatment and the stratification factor at randomization as explanatory variables.

Time to CDI recurrence is defined as the number of days from enema administration to first assessment indicating recurrence for those subjects who were deemed Treatment Failures with CDI recurrence. All subjects who are Indeterminate or discontinued for any reason prior to assessment of efficacy will be censored at the last assessment date at/prior to Week 8. For the analysis of Time to CDI recurrence within 8 weeks, all subjects considered as a treatment success will be censored at the date of their 8-week assessment. For the analysis of Time to CDI

recurrence through 6 months, all subjects considered to have achieved sustained clinical response will be censored at the date of their 6-month assessment.

Finally, the sensitivity of the primary efficacy endpoint will be assessed in a multivariate logistic regression adjusting for possible interactions of the following covariates with treatment group: age (< 65 years, \geq 65 years), sex (Female, Male), race group (White, Non-white), ethnicity (Hispanic-Latino, not Hispanic-Latino), site geography (outside the US, Eastern US*, Southern US*, Northern US*, Western US*), randomization strata (i.e., treatment received at the qualifying event) and number of previous episodes of CDI recurrence at baseline. Other baseline variables will be compared for balance using the appropriate statistical test. This analysis will be performed on all analysis populations where at least 20 subjects in each sub-group are available for analysis to fully understand the observed treatment effect.

*States included in the identified US geographical regions are as follows:

- Eastern US: Connecticut, Delaware, District of Columbia, Maine, Maryland, Massachusetts, New Hampshire, New Jersey, New York, Ohio, Pennsylvania, Rhode Island, Vermont, Virginia, West Virginia
- Southern US: Alabama, Arkansas, Georgia, Florida, Kansas, Kentucky, Louisiana, Mississippi, North Carolina, Oklahoma, South Carolina, Tennessee, Texas
- Northern US: Illinois, Indiana, Iowa, Michigan, Minnesota, Missouri, Nebraska, North Dakota, South Dakota, Wisconsin
- Western US: Arizona, California, Colorado, Idaho, Montana, Nevada, New Mexico, Oregon, Utah, Washington, Wyoming

